# 9 STATISTICAL CONSIDERATIONS

## 9.1 General Design Issues

This study is a double-blind, randomized, placebo-controlled parallel group study. The primary objective is to obtain estimates of the effect of the study drug on cerebral NAA. Secondary and safety and tolerability measures will also be collected and compared between treatment groups.

## 9.2 Sample Size and Randomization

Forty-eight (48) subjects will be enrolled and randomized 2:1 to either treatment (n=32) or placebo (n=16). Our sample size of 48 subjects was determined consistent with our primary objective of estimation rather than hypothesis testing; the latter (hypothesis testing) we deemed more appropriate for confirmatory studies that we anticipate will follow this initial pilot trial. We anticipate the results of this study will inform the power calculations of those subsequent trials. Thus, we base our sample size justification on providing sufficient precision for estimating our effect with a 95% confidence interval. Assuming 32 subjects in the active group and 16 subjects in the placebo group and allowing for up to 15% attrition our sample size of 48 will enable estimates of the difference in cerebral NAA to be within approximately 0.69 standard deviations for a 95% confidence interval. This magnitude of the half-width of the confidence intervals (0.69 standard deviations) was derived from the confidence interval formula for estimating a difference between two treatment means using quantiles from a t distribution, using the pooled variance formula for a common variance, and post-attrition group sizes of 27 and 13 subjects. From Kalra, Cashman, Genge, and Arnold (1998, NeuroReport 9, 1757-61), estimated standard deviations for changes in NAA/Cr both in treated and control conditions were approximately 0.2. For the regression techniques to apply that we described below, we anticipate our results will produce similar sized magnitudes for estimating the standard deviations for this study (i.e., we anticipate our confidence intervals to be within a magnitude of approximately 0.14).

#### 9.2.1 Treatment Assignment Procedures

Subjects will be randomly assigned to treatment or placebo based on the randomization schedule developed by the lead study statistician. This procedure will be balanced within random blocks to increase the balance between treatments over the recruitment period. Treatment order within blocks will be determined by randomly selecting and sorting random draws from a uniform distribution using a pseudo-random number generator on a statistical software package.

## 9.3 Interim analyses and Stopping Rules

No interim analyses or stopping rules are planned for this trial.

#### 9.4 Outcomes

#### 9.4.1 Primary outcome

MR spectra will be analyzed to determine the concentration of NAA (as a continuous measure) using the LCModel package and in-house MR data processing pipeline to correct for tissue fraction in each voxel using the segmented MPRAGE MRI corresponding to the CSI slab.

#### 9.4.2 Exploratory outcomes

MRS Measures: In addition to NAA, we will assess the concentration (as continuous measures) of several other neurochemicals including glutathione, creatine, choline, myoinositol, and glutamate+glutamine from the same location using a multiple-quantum filtered CSI sequence.

Cerebral metabolism by FDG PET: PET images will be analyzed using custom software written for Statistical Parametric Mapping (SPM12). Pre- and post-intervention P images will be co-registered. A priori regions of interest masks from the Automated Anatomic Labeling series will be inverse warped to match native space images. The PET images will be standardized to the uptake value of the cerebellum and standardized uptake value ratios (SUVR) will be calculated from native-space ROIs.

Systemic metabolic measures will be continuous measures.

- Systemic NAA levels (in blood and urine)
- o Lipids (total cholesterol, LDL, HDL)
- Plasma beta-hydroxybutyrate
- Hemoglobin A1c
- Glucose and insulin Area Under the Curves (tolerance testing)
- Catabolic/Anabolic state [activated AKT and MTOR]
- Mitochondrial function measures [platelet cytochrome oxidase and citrate synthase]
- o Inflammatory mechanisms [MCP-1, eotaxin, TNF alpha, CRP]
- Body composition (DEXA scanning for fat and lean mass)
- Resting metabolic rate (indirect calorimetry).

Cognitive performance will be assessed using the ADAS-cog 14 (total score) and individual performance scores on Trailmaking A and B, Stroop Word Color test, and Logical Memory I and II.

#### 9.4.3 Safety Outcomes

We will examine the incidence and severity of AEs and the rate of discontinuations due to AEs. Additionally, we will examine changes in cognitive performance, body weight, and laboratory values observed during the course of the study.

#### 9.5 Data Analyses

Unless otherwise specified, all efficacy analyses will be carried out on all subjects enrolled. Continuous variables will be summarized (using number of participants, mean, standard deviation, and percentiles) by treatment group and visit. For baseline, all end-ofstudy measurements, the changes, or relative changes from baseline will be presented by treatment group for all efficacy variables to be analyzed. Categorical variables will be summarized, by treatment group, using frequency count and the percentage of participants in each category. This will facilitate assessment for independence in these baseline measures across treatment groups, which we anticipate given treatment will be allocated at random. (Notably, this inference of independence is equivalent to testing for no difference in proportional distributions across treatment groups.)

The primary objective is estimation, so we will generate 95% confidence intervals for "adjusted" treatment means and their differences based on the formulas analogous to an analysis of covariance (ANCOVA)/ordinary least squares (OLS) regression model hypothesis testing procedure. For these models we will use the baseline measure as a covariate, including assigned treatment as a fixed effect, and change from baseline measure (i.e., follow-up minus baseline) as the response/outcome measure. To deem the adequacy of normal distribution quantiles for confidence interval estimation we will carry out the residual analyses to assess the assumptions of that test for each measure. In the event that the residual diagnostics (including residual vs. predicted value plots, quantilequantile plots, etc.) do not conform to the underlying normality and other assumptions of this test, we will revert to nonparametric rank-based approach using ANCOVA as described above with ranks used instead for the response to derive model-based p-values. For categorical measures, we will use confidence intervals based on the Wald estimate of the standard error in comparisons of proportions between assigned treatment for dichotomous responses/outcomes if the expected cell counts (under the hypothesis of independence) for corresponding contingency tables are at least five in most (>80%) cells. If the expected cell counts are not sufficiently large, we will instead estimate using exact, Clopper-Pearson confidence intervals.

To assess scan-rescan reliability for NAA on the 12 subjects, we will estimate the variance in the difference scores between each of these 12 subjects' pre-randomization MRI/MRS scans. This will provide information on intra-individual scan-to-scan variation for consideration as we interpret differences (time one minus time two) estimated between treatment groups.

As only pre- and post-treatment measures are obtained, subjects missing post-treatment follow-up measures will be excluded from these analyses.

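### If residual diagnostics are judged to fail for cerebral NAA, the plan commits only to rank-based p-values and not to a baseline-adjusted NAA difference with a 95% CI

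*Combined protocol and SAP*

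**What the plan says.** Section 9.1 states the aim: "The primary objective is to obtain estimates of the effect of the study drug on cerebral NAA". Section 9.2 sizes the trial "consistent with our primary objective of estimation rather than hypothesis testing" and leaves testing to later confirmatory studies. The planned half-width of about 0.69 SD "was derived from the confidence interval formula for estimating a difference between two treatment means using quantiles from a t distribution", with 27 and 13 participants after attrition.

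Section 9.5 follows this through: "The primary objective is estimation, so we will generate 95% confidence intervals" for adjusted treatment means and their differences. These come from an ANCOVA of change on baseline and assigned treatment. The check on those intervals is stated next: "To deem the adequacy of normal distribution quantiles for confidence interval estimation we will carry out the residual analyses". It applies to every measure, so it covers the primary outcome of Section 9.4.1. If the diagnostics do not conform, "we will revert to nonparametric rank-based approach using ANCOVA as described above with ranks used instead for the response to derive model-based p-values".

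Two other parts of Section 9.5 matter here. Descriptive results are produced in any case: "Continuous variables will be summarized (using number of participants, mean, standard deviation, and percentiles) by treatment group and visit", and changes from baseline are also shown by arm. For categorical measures, when the large-sample interval is doubtful, the fallback is an exact Clopper-Pearson interval.

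**The concern.** The fallback changes the kind of answer that the trial gives. Before the diagnostics, the stated product is an adjusted NAA difference with a 95% CI. After a failed diagnostic, the only inference named is a p-value, which is what Section 9.2 defers to later studies. A treatment coefficient from ranked responses is in rank units and cannot be read as an NAA difference. The precision target of 0.69 SD therefore has no counterpart in that branch.

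The contrast with the categorical fallback is telling. There the plan moves from one interval to another; for continuous outcomes, including the primary one, it moves from an interval to a p-value. The trigger is a judgement on plots with no threshold. Whether an adjusted interval is reported could thus be decided after the data are seen.

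**Working it through.** **1. The plan's precision figure.** Inputs from Section 9.2: 27 and 13 analysed, pooled variance, t quantile, SD of change about 0.2 (for NAA/Cr).

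Half-width = t(0.975, 38) × √(1/27 + 1/13) = 2.024 × 0.3376 = 0.683 SD. Times 0.2, this is 0.137. Both agree with the stated 0.69 SD and 0.14. With the ANCOVA's 37 df the multiplier is 0.684. The formula is unadjusted; Section 9.2 only anticipates similar precision from the regression.

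**2. A rank coefficient does not give an NAA difference.** In one simulated data set (27 versus 13), the change y was analysed as y, 10y and exp(3y). The rank-ANCOVA coefficient was 11.27 (SE 3.58) each time. The least-squares differences were 0.243, 2.43 and 1.10. One rank result is compatible with very different effects on the original scale.

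**3. Does non-normality require dropping the interval?** Simulation: change = 0.5 × treatment − 0.3 × baseline + error, baseline SD 1, error SD 1, 27 versus 13, 20,000 runs per case, 95% intervals with t on 37 df. The slope, baseline SD and error shapes are assumptions, since the documents give none for cerebral NAA. A flag means Shapiro-Wilk or studentized Breusch-Pagan p < 0.05, an assumed stand-in for the plan's plots.

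| Errors | OLS coverage | Flagged | OLS coverage when flagged |
|---|---|---|---|
| Normal | 95.1% | 9% | 94.9% |
| t, 5 df | 95.0% | 31% | 95.6% |
| t, 3 df | 95.6% | 54% | 95.9% |
| Log-normal (σ 0.75) | 95.8% | 97% | 95.9% |

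The Monte Carlo standard error is about 0.15 points overall and up to 0.5 points among flagged data sets. The interval keeps its coverage in the very data sets that would lead the plan away from it.

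**4. Unequal variance, as a limit on step 3.** Suppose the placebo SD were 1.5 times the active SD. The expected pooled variance is (26 × 1 + 12 × 2.25)/38 = 1.395, so the pooled SE is about √1.395 × 0.3376 = 0.399. The true SE is √(1/27 + 2.25/13) = 0.458. The pooled SE is too small by a factor of 0.87. Half-widths below are in units of the unscaled arm's residual SD.

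| Case | OLS coverage (half-width) | HC3 coverage (half-width) |
|---|---|---|
| Normal, equal SDs | 95.1% (0.69) | not listed (0.72) |
| Placebo SD 1.2× | 93.5% (0.73) | 95.4% (0.82) |
| Placebo SD 1.5× | 91.4% (0.81) | 95.0% (0.97) |
| Active SD 1.5× | 97.3% (0.94) | 95.9% (0.86) |
| Log-normal, placebo SD 1.5× | 91.7% (0.78) | 93.5% (0.91) |

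A separate normal-error run with equal SDs (5,000 data sets per setting) gave HC3 coverage of 94.9% to 95.5%.

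At placebo SD 1.5×, the stand-in tests flag only 33% of data sets, and switching to HC3 only when flagged covers 92.9%. Letting diagnostics choose the interval is therefore a poor remedy.

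**The case against.** The strongest reply is that the interval commitment in Section 9.5 carries no condition, and that the fallback names only p-values. On that reading it replaces a test and leaves the interval standing. This is possible, and part of it stands: the text does not forbid the OLS interval. But the diagnostics are tied expressly to interval estimation, and the wording of the fallback suggests replacement, so the plan does not commit to the interval either.

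The second reply is that NAA-scale information survives, and this also stands in part. Group sizes, means and SDs are tabulated, as are changes by arm, so a crude unadjusted interval could be worked out. A reader might infer that the fallback would leave nothing for the purpose stated in Section 9.2: "We anticipate the results of this study will inform the power calculations of those subsequent trials". The documents do not support that. What is uncommitted is the adjusted difference and its interval.

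Third, a reader might take the 91% to 92% coverage figures as a defect of the planned OLS interval. They rest on an assumed variance ratio. The only evidence in the documents, the cited NAA/Cr figures in Section 9.2, gives an SD of change of about 0.2 in both treated and control conditions. NAA/Cr is not the concentration named in Section 9.4.1, so this does not settle the matter, but it does not suggest a ratio of 1.5.

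**Conclusion.** The point holds as a conditional, moderate gap that should be fixed. If diagnostics are judged to fail for cerebral NAA, the stated rule leads to p-values, and no baseline-adjusted NAA-scale difference or CI is committed to, in a trial whose primary objective and sample size both rest on such an interval. This conclusion comes from the text and does not depend on the simulations. How often the branch would be entered is unknown: the trigger is a visual judgement and the documents give no residual distribution for NAA.

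The simulations add one thing. Under the assumed error shapes, non-normality gives no reason to abandon the OLS interval at 27 versus 13.

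Two stronger readings go too far. One is that the plan discards the estimate; it only fails to promise it. The other is that the same rule must govern every exploratory continuous outcome. The estimation argument and the calculations concern cerebral NAA, and whether a mean difference is the best summary of, say, CRP or Trailmaking needs its own judgement.

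**What to change.** For the primary outcome, replace the fallback sentence in Section 9.5 with:

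> The baseline-adjusted mean difference in change in cerebral NAA and its OLS 95% CI on the original scale are reported as the primary result whatever the residual diagnostics show. An HC3 robust 95% CI for the same difference is reported alongside it in all cases as a prespecified sensitivity analysis, and rank ANCOVA is supportive only.

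The plots should be reported but should not decide which interval is primary. Leave the exploratory outcomes to be settled one by one.

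The cost is a few sentences of text and slightly more analysis, with no new data. The HC3 interval is a little wider when assumptions hold (about 0.72 versus 0.69 SD). Keeping OLS as primary accepts undercoverage of about 91% to 92% if the placebo SD were 1.5 times the active SD. The HC3 interval beside it would tend to show this by its greater width (0.97 versus 0.81 on average). HC3 is not a full cure, since it covers about 93% when strong skew and unequal variance occur together.

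### Where the expected-count rule admits the Wald interval, the between-arm difference in a common dichotomous outcome such as any AE is covered about 93% of the time rather than 95% (minor)

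*Combined protocol and SAP*

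**What the plan says.** Section 9.5 gives one rule for dichotomous outcomes: "we will use confidence intervals based on the Wald estimate of the standard error in comparisons of proportions between assigned treatment". This applies if the expected counts, computed under independence, "are at least five in most (>80%) cells". The fallback is also stated: "If the expected cell counts are not sufficiently large, we will instead estimate using exact, Clopper-Pearson confidence intervals".

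Section 9.4.3 lists the safety outcomes without naming an interval: "We will examine the incidence and severity of AEs and the rate of discontinuations due to AEs". Section 9.1 adds: "Secondary and safety and tolerability measures will also be collected and compared between treatment groups". No other method for comparing AE proportions appears, so the rule in 9.5 is the one that would apply to them.

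Section 9.2 fixes the group sizes: "Forty-eight (48) subjects will be enrolled and randomized 2:1 to either treatment (n=32) or placebo (n=16"). For precision it works with "post-attrition group sizes of 27 and 13 subjects".

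The 95% level is written for the continuous analysis in 9.5 (adjusted means and their differences) and in 9.2. The sentence on proportions gives no level, and 95% is the natural reading of the paragraph.

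**The concern.** The expected-count rule is there to decide when a large-sample interval can be trusted. Expected counts of five in each cell are a familiar guide for a chi-square test. They do not ensure that a Wald interval for a difference in proportions reaches its nominal coverage when one arm has 16 participants. The Wald interval is centred on the raw difference, is symmetric about it, and uses a variance that falls to zero in an arm where everyone or no one has the event.

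The trial is justified by interval estimation rather than by testing, and safety and tolerability is a stated objective (Précis; sections 1.3 and 3.3). At stake is whether an interval reported as 95% for a common safety outcome, such as the difference in the proportion with any AE, misses the true difference more often than its label says.

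**Working it through.** **Inputs.** Group sizes 32 and 16, and post-attrition sizes 27 and 13 (section 9.2). Wald interval, count rule and exact fallback (section 9.5). Level 95%, inferred as above. AE rates: the documents give none, so true rates of 30% to 70% in each arm are an assumption.

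**1. The plan's own precision figure.** This concerns cerebral NAA, not proportions, and is reproduced only to confirm the group sizes. t(0.975, 38) × √(1/27 + 1/13) = 2.024 × 0.3376 = 0.683 SD. The plan states about 0.69 SD, so the agreement is within about 1%. No precision or coverage figure is given for proportions.

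**2. When the Wald branch applies.** In a 2×2 table three qualifying cells out of four is 75%, so a requirement of more than 80% means all four. With m events in total, the smallest expected count is 16 × min(m, 48 − m)/48. Setting this to at least 5 gives min(m, 48 − m) ≥ 15, so m runs from 15 to 33, an overall incidence of 31% to 69%. At 27 and 13, the condition 13 × min(m, 40 − m)/40 ≥ 5 gives m from 16 to 24.

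**3. Probability of reaching the branch at 32 and 16** (assumed true rates, dapagliflozin/placebo):

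| Rates | Probability |
|---|---|
| 10%/10% | under 0.01% |
| 20%/10% | 0.9% |
| 20%/20% | 4.4% |
| 30%/20% | 28% |
| 30%/30% | 48% |
| 40%/40% | 92% |
| 75%/70% | 28% |
| 80%/80% | 4.4% |

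**4. Coverage within the branch.** All 33 × 17 binomial outcomes were enumerated and the tables meeting the rule kept. Coverage was computed on a grid of true rates from 0.30 to 0.70 in steps of 0.05 in each arm (81 points).

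- Wald: p1 − p2 ± 1.96 × √(p1q1/n1 + p2q2/n2).
- Newcombe, with Wilson limits (l, u) in each arm: lower = d − √((p1 − l1)² + (u2 − p2)²); upper = d + √((u1 − p1)² + (p2 − l2)²), where d = p1 − p2.

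| Sizes | Interval | Mean coverage | Range | Mean full width |
|---|---|---|---|---|
| 32, 16 | Wald | 93.1% | 92.1–94.2% | 0.568 |
| 32, 16 | Newcombe | 94.7% | 93.9–95.3% | 0.526 |
| 27, 13 | Wald | 92.7% | 91.1–93.7% | 0.629 |
| 27, 13 | Newcombe | 94.7% | 93.6–95.9% | 0.573 |

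At 32 and 16, Wald is below 95% at every grid point: for example 93.9% at 40%/40%, 93.8% at 50%/50% and 92.6% at 60%/40%. A different grid (overall rates 31% to 69%, differences up to 0.30) gives the same Wald mean of 93.1%, with a range of 90.9% to 94.2%.

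**5. Source of the shortfall.** Newcombe covers better while being shorter on average, so average width is not the fault. In a typical table, 16/32 against 8/16, the Wald half-width is 1.96 × √(0.25/32 + 0.25/16) = 1.96 × 0.1531 = 0.300. The Wilson limits are 0.336–0.664 and 0.280–0.720, so the Newcombe half-width is √(0.164² + 0.220²) = 0.274. If the Wald centre is kept, the half-width has to grow by about 8% to reach 94.9% on average (second grid).

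**6. An extreme table.** 17/32 against 16/16 has 33 events and a smallest expected count of 16 × 15/48 = 5.0, so it passes the rule. The placebo arm then adds no variance. Wald gives −0.64 to −0.30 and Newcombe −0.64 to −0.22, so here Newcombe is the wider. With both true rates at 60%, this table has a probability of about 0.003%.

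**The case against.** Wald with an expected-count condition and an exact fallback is a conventional, prespecified choice, and the plan has anticipated the small-sample problem. The trial is a pilot with no safety test or threshold and no interim analysis (section 9.3), and stopping for safety rests on the safety officer's judgment (section 7.6). About two points of coverage on an interval roughly 0.57 wide changes no decision. All of this stands, and it sets the rank of the point. It does not remove the shortfall: in a plan whose product is interval estimates, coverage is the property being offered.

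A reader might infer three stronger things, none of which is supported.

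- That the Wald intervals are too narrow. On average they are wider than the better-covering alternative.
- That the main safety intervals are affected. The branch needs 31% to 69% overall incidence. Section 2.3 speaks only of small increases in particular AEs. At rates up to about 20% in both arms, the branch is reached in under 5% of trials.
- That the any-AE rate is likely to lie in that range. The documents give no AE rate, and at 80% in both arms the branch would be reached only 4.4% of the time.

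Nor should the 17/32 against 16/16 table be taken as typical. It shows what the rule admits, not what is likely to be seen.

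**Conclusion.** The point holds as a minor one. For outcomes common enough to pass the count rule, a nominal 95% Wald interval for the difference misses the true difference about 6.9% of the time at 32 and 16 (100 − 93.1), and about 7.3% at 27 and 13 (100 − 92.7), instead of 5%.

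This rests on three assumptions: true rates of 30% to 70% in each arm; a 95% level for proportions, which the text implies but does not state; and section 9.5 governing AE proportions, since no other method is given for them. The 27 and 13 figures apply only if the denominators shrink with attrition.

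**What to change.** In section 9.5, where the expected-count condition is met, replace the Wald interval for between-arm differences in proportions with the two-sided 95% Newcombe interval built from Wilson score limits. State the 95% level in the same sentence.

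The cost is one sentence and a standard software option, with no effect on trial conduct or sample size. Intervals become shorter on average (mean full width 0.526 against 0.568 at 32 and 16) and wider only in some extreme tables.

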## 7.3 Adverse Events and Serious Adverse Events

An **adverse event (AE)** is generally defined as any unfavorable and unintended diagnosis, symptom, sign (including an abnormal laboratory finding), syndrome or disease, which occurs during the study, having been absent at baseline, or if present at baseline, appears to worsen. Adverse events are to be recording regardless of their relationship to the study intervention.

A serious adverse event (SAE) is generally defined as any untoward medical occurrence, occurring after the signing of the informed consent through the follow-up period that fulfils one or more of the following criteria: that results in death, is life threatening, requires hospitalization or prolongation of existing hospitalization, results in persistent or significant disability/incapacity, , an important medical event that may jeopardize the patient or may require medical intervention to prevent one of the outcomes listed above.. or is a congenital anomaly.

All SAEs will be reported, whether or not considered causally related to the IP, or to the study procedure(s). All SAEs will be recorded in the CRF. The causality of SAEs (their relationship to all study treatment/procedures) will be assessed by the investigator(s) and communicated to AstraZeneca.

AEs and SAEs will be collected from the time of informed consent until end of study (week 14).

The following variables will be collected for each AE;

- AE term, using the diagnosis if known, or signs or symptoms when diagnosis is not known
- The date when the AE started and stopped
- Maximum intensity (mild, moderate or severe)
- Whether the AE is serious or not
- Investigator causality rating against the Investigational Product (yes or no)
- Action taken with regard to investigational product
- Outcome.
- In addition, the following variables will be collected for SAEs:

- Date AE met criteria for serious AE
- Date Investigator became aware of serious AE
- Criterion that classifies AE as serious
- Date of hospitalization
- Date of discharge
- Probable cause of death
- Date of death
- Autopsy performed
- Causality assessment in relation to Study procedure(s)
- Description of AE.

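### For sparse 2x2 tables, Section 9.5 replaces the between-arm interval with Clopper-Pearson, a one-proportion interval, so most AE comparisons have no pre-specified interval

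*Combined protocol and SAP*

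**What the plan says.** Section 9.5 (Data Analyses) plans, for dichotomous outcomes, "confidence intervals based on the Wald estimate of the standard error in comparisons of proportions between assigned treatment". The condition for using them is "if the expected cell counts (under the hypothesis of independence) for corresponding contingency tables are at least five in most (>80%) cells". If it fails, "we will instead estimate using exact, Clopper-Pearson confidence intervals". The same section says: "Categorical variables will be summarized, by treatment group, using frequency count and the percentage of participants in each category".

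Section 9.1 says that "safety and tolerability measures will also be collected and compared between treatment groups". Section 9.4.3 lists the incidence and severity of AEs and "the rate of discontinuations due to AEs". Sections 9.4.1 and 9.4.2 define the other outcomes as continuous measures or scores; for example, "Systemic metabolic measures will be continuous measures". Section 2.3 expects small increases in urinary tract infections, genital infections and some other AEs on dapagliflozin.

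**The concern.** The Wald clause makes the between-arm comparison of proportions the quantity to be estimated. The next sentence offers Clopper-Pearson in its place. That method inverts the exact binomial test for a single proportion, so it yields an interval for each arm and none for the contrast. No other section names an exact or score-based two-sample method.

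Because the NAA, other MRS, PET, systemic and cognitive outcomes are continuous or scores, the rule bears mainly on AE incidence and discontinuations due to AEs. Safety and tolerability is a stated objective, and with small increases expected the quantity of interest is the excess on drug. As written, the plan pre-specifies no interval for that excess in sparse tables. One could be computed later from the reported counts, but by a method chosen after the data were seen.

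**Working it through.** **Inputs.** Arm sizes are 32 and 16 (Section 9.2). AEs are collected from consent to week 14 (Section 7.3), and data available on participants who stop are kept (Section 8), so the full arm sizes are used. The 95% level is stated for the primary estimate; Section 9.5 gives no separate level for dichotomous outcomes, so 95% is assumed. AE rates by arm are not given and are assumed over a range.

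**The plan's own figure.** Section 9.2 gives a precision figure only for NAA, a half-width of about 0.69 SD. It recomputes as t(0.975, 38) x sqrt(1/27 + 1/13) = 0.683. The plan gives no precision figure for dichotomous outcomes.

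**When the substitute applies.** A 2x2 table has four cells. Three of four is 75%, so more than 80% means all four. Let k be the number of the 48 participants with the event. The smallest expected counts are in the placebo arm:

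- events: 16k/48 >= 5, so k >= 15
- non-events: 16(48 - k)/48 >= 5, so k <= 33

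Wald is allowed only for k = 15 to 33, that is 31% to 69% of participants. With the post-attrition sizes of 27 and 13 the range narrows to 16 to 24 of 40.

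**How often.** All 33 x 17 possible tables were enumerated with exact binomial probabilities, summing those with k outside 15 to 33:

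| Assumed true rates, active / placebo | Probability of the substitute |
|---|---|
| 10% / 5% | above 99.9% |
| 20% / 10% | 99.1% |
| 25% / 15% | 92.2% |
| 30% / 20% | 71.7% |
| 35% / 25% | 42.1% |
| 40% / 30% | 17.6% |
| 50% / 40% | 1.1% |
| 20% / 20% | 95.6% |
| 30% / 30% | 52.1% |

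**What it delivers, for 4/32 against 0/16** (illustrative counts; k = 4, so Wald is not allowed).

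- Clopper-Pearson: 3.5% to 29.0% on drug. On placebo it is 0% to 20.6%, since 1 - 0.025^(1/16) = 0.206. There is no interval for the difference of 12.5 points.
- Newcombe: the Wilson limits are 5.0% to 28.1% and 0% to 19.4%. Lower limit: 0.125 - sqrt((0.125 - 0.050)^2 + 0.194^2) = -0.083. Upper limit: 0.125 + (0.281 - 0.125) = +0.281.
- Other two-sample intervals for the difference, in points:

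| Method | 95% interval | Width |
|---|---|---|
| Newcombe | -8.3 to +28.1 | 36.4 |
| Miettinen-Nurminen | -8.1 to +28.3 | 36.4 |
| Exact unconditional, score-ordered | -9.4 to +29.0 | about 38 |
| Exact unconditional, ordered by raw difference | -18.9 to +42.3 | about 61 |
| Wald, if carried over | +1.0 to +24.0 | 23.0 |

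The Wald row is 0.125 +/- 1.96 x sqrt(0.125 x 0.875/32); the placebo arm contributes zero variance. It is the only one of the five that excludes zero. Staying with Wald is therefore no remedy, and the choice of method can change the reading.

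**Coverage of the replacements.** Among tables that reach the substitute, at assumed rates from 10%/5% to 40%/30%, coverage is 94.5% to 98.5% for Newcombe (lowest at 40%/30%) and 95.8% to 98.5% for Miettinen-Nurminen.

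**The case against.** The best defence has four parts.

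- **No interval is promised for AEs.** Section 9.1 says only that safety measures will be compared, and Section 9.4.3 says they will be examined. This is true of those two sections. But Section 9.5 plans an interval for the comparison of proportions, and the sparse-table sentence is written as its replacement.
- **Section 9.5 does not mention AEs.** The link is by elimination, because the other listed outcomes are continuous or scores. That is an inference. If the section does not govern AEs, the plan has no stated method for comparing them at all.
- **The authors may have meant to stop at arm-wise estimates when counts are small.** That is defensible in a pilot of 48, but the plan does not say so, and the comparison in Section 9.1 would still have no interval. If another exact method was meant, it is not named.
- **Little depends on it.** This largely stands. Section 9.3 plans no interim analysis or stopping rule, safety decisions rest on the safety officer's judgement, and the two-sample intervals in the example are wide and include zero. Newcombe and Miettinen-Nurminen differ by only about 0.2 points per limit. The wider spread to raw-difference exact or Wald is why the method should still be fixed in advance.

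The probabilities depend on assumed rates; only the 15-to-33 range follows from the plan itself.

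**Conclusion.** The concern holds. The sparse-table branch of Section 9.5 names a method that cannot estimate the between-arm comparison it is meant to replace. It governs any dichotomous outcome seen in 14 or fewer, or 34 or more, of the 48 participants. At assumed rates up to 25% on drug and 15% on placebo, it applies with probability of at least 92%. At 50% and 40% it almost never applies, so a common outcome such as any AE may stay on Wald.

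The consequence is confined to dichotomous outcomes, mainly AE incidence and discontinuations due to AEs. The plan should be corrected on this point, but the trial's main estimate does not depend on it. The conclusion rests on reading Section 9.5 as covering AEs and on analysing 32 and 16 participants; with 27 and 13 the substitute would apply to a wider range of event proportions.

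**What to change.** In Section 9.5, name a two-sample 95% interval for the risk difference when the expected-count condition fails, and keep Clopper-Pearson for the incidence in each arm. Newcombe or Miettinen-Nurminen would serve. If exactness is wanted, as the present wording suggests, specify an exact unconditional interval and its ordering, since in the example the ordering changes the width from about 38 to about 61 points. If arm-wise reporting alone is intended, say so, and state that no interval will be given for the comparison.

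The cost is one sentence and standard software, with no effect on participants or trial conduct.
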